4.4 Patient Identification and Enrollment

Patients must be able to provide written informed consent and meet all inclusion criteria and none of the exclusion criteria. No waivers of inclusion or exclusion criteria will be granted by the Investigator and Sponsor or its designee for any patient enrolled in the study. Before enrolling a patient, all eligibility criteria must be satisfied. Patients who qualify for Part 1A of the study will

be enrolled into the first available cohort. In Part 1B, approximately 3 gastric cancer patients may be enrolled at each dose level, starting one dose level below the current Part 1A dose. The Sponsor and Investigators may elect to enroll up to an additional 3 patients per dose level whose tumors overexpress FGFR2b. In Part 2, approximately 20 patients with gastric cancer with strong FGFR2b overexpression (IHC 3+ \geq 10%, Cohort A) will be enrolled. A cohort of patients with FGFR2b-selected non-gastric solid tumors will also be enrolled in Part 2 (Cohort F), including FGFR2b-selected bladder cancer which has an accompanying validated IHC assay. Patients with additional tumor types may be enrolled, contingent on the development of an accompanying validated laboratory test for the analysis of FGFR2b expression.

The Investigator may repeat qualifying lab tests and vitals/ECGs prior to enrollment if a non-qualifying finding is considered an error or an acute finding is likely to meet eligibility criteria on repeat testing.

4.5 Pre-Study Screening (Part 1B and Part 2)

Potential Part 1B and Part 2 patients may elect to consent to tumor tissue analysis at any time prior to full assessment of eligibility for enrollment to have their tumor tissue sent to a third party laboratory in the United States for FGFR2b expression and *FGFR2* amplification analysis. Approximately 10 unstained slides or formalin-fixed, paraffin-embedded tumor tissue must be available for determination of FGFR2b overexpression. For Part 2, once a potential study patient's tumor is known to overexpress FGFR2b, the patient may be given the opportunity to consent to full study participation and will undergo screening to ensure the eligibility criteria are met. The tumor tissue analysis may be done at any time prior to enrollment in the study, if patients have:

- Confirmed diagnosis of either gastric or gastroesophageal cancer, bladder cancer or other locally advanced or metastatic non-gastric solid tumor with an accompanying validated laboratory test for the analysis of FGFR2b expression
- Age \geq 18 years
- Performance status (PS) \leq 1 on the ECOG Performance Status Scale (see [Appendix 3](#)) or Investigator's opinion that PS will have recovered to this level by the time of enrollment
- The patient will have signed and dated the Institutional Review Board/Ethics Committee-approved consent document prior to any protocol-specific screening procedures being performed

Note: Patients should not undergo any study-related procedures until full study consent has been obtained.

5. Study Drug

5.1 Identity

FPA144 drug product is a sterile aqueous solution supplied in single-use glass vials. The composition of the drug product contains 20 mg/mL active ingredient, 20 mM L-histidine, 270 mM sucrose, 0.01% polysorbate 20 at pH 6.0. The container-closure system consists of a 10 mL Type I borosilicate tubing glass vial, a 20 mm bromobutyl rubber stopper, and a 20 mm flip-off seal. The final drug product will be provided as refrigerated liquid 5ml fill in ISO 6R vials, which is diluted for administration per instructions provided in a separate Pharmacy Manual.

5.2 Administration

FPA144 will be administered only to patients in this study using procedures described in this protocol.

The dose of FPA144 is based on body weight at Cycle 1 Day 1 and adjusted if the patient's weight changes > 10% from Cycle 1 Day 1.

A pharmacist (or other responsible person) will prepare the solution for administration. After calculating the number of vials, based on the patient's weight, the study drug product will be diluted in a 0.9% sodium chloride solution. Prepared FPA144 should be administered ≤8 hours after preparation (ambient temperature). FPA144 will be administered under medical supervision over approximately 30-minute IV infusion via a peripheral vein or central venous catheter. The IV administration set for FPA144 infusion must contain a 0.22-µm in-line filter or a 0.22-µm syringe filter.

Infusion of FPA144 must be stopped, reduced, interrupted, or discontinued per Section 5.4.6. If a patient experiences an infusion reaction, the patient's vital signs (temperature, blood pressure, pulse, and respiration rate) should be monitored during the infusion as well as every 30 minutes after the infusion for a minimum of 2 hours and until resolution of the infusion reaction.

Further instructions on drug preparation and administration are in the Pharmacy Manual.

5.3 Packaging, Labeling, and Storage

Study drug will be packaged as a 5 ml fill in ISO 6R vials by the Sponsor (or designee) according to all local legal requirements. Study drug will be labeled in accordance with applicable regulatory requirements.

All study drug supplies must be stored refrigerated at 2°– 8°C in accordance with the manufacturer's instructions as provided in the Pharmacy Manual. Until dispensed to patients, the study drug will be stored in a securely locked area, accessible to authorized personnel only.

5.4 Starting Dose and Dose Modifications

The starting dose level of FPA144 and subsequent dose escalations between cohorts in Parts 1A and 1B are described in Section 3.1.2. The dose of FPA144 in Part 2, the expansion phase of the study, will be determined by evaluation of the data from Part 1A of the study.

5.4.1 Dose Escalation of FPA144 between Cohorts (Part 1A)

Dose escalation to the next cohort will only start after the preceding dose cohort has completed the DLT period. Twenty-eight days (DLT period) of safety data must be available on at least 3 safety-evaluable patients prior to a potential dose-escalation decision by the CRC. In the event that a patient in a cohort is lacking adequate safety data (e.g., due to early withdrawal from study or poor compliance with the protocol), an additional patient will be enrolled to the cohort.

Dose escalation in each successive dose cohort will proceed in a stepwise fashion. All relevant safety information for the first cohort or the preceding dose cohort will be reviewed by the CRC (see Section 9.9).

During dosing, the CRC may decide to stop dosing a patient or the complete cohort for safety reasons.

Dose escalation is planned to continue until dose-limiting toxicities occur in 2 or more patients in a cohort. The decision to discontinue dose escalation will be made jointly by the Sponsor and Investigator(s) based on reaching MTD or a dose level that achieves target serum concentration of FPA144.

Once the MTD or RD has been reached, 3-10 additional gastric cancer patients *may* be added prior to commencing Part 2, to further explore the safety and PK at this dose level.

The dose escalation decision rules are summarized in Table 2.

Table 2: Decision Criteria for Escalation

Number of Patients with DLTs	Action
0/3	Open next cohort
1/3	Enroll 3 more in same cohort
≥2/3	Stop enrollment. Enter three more patients at dose level below, if only 3 were previously entered
1/6	Open next cohort
≥2/6	Stop enrollment. Enter three more patients at dose level below, if only 3 were previously entered

5.4.2 Dose Escalation of FPA144 (Part 1B)

In a staggered fashion with Part 1A dose escalation, patients in Part 1B will be enrolled at one dose level below the current highest dose level cohort being studied in Part 1A. For example, if the current dose level in Part 1A being studied is 3 mg/kg, enrollment of Part 1B patients will be at the 1 mg/kg dose level; if the current dose level being studied in Part 1A is 6 mg/kg, enrollment of Part 1B patients will be at the 3 mg/kg dose level.

During dosing, the CRC may decide to stop dosing a patient or the complete cohort for safety reasons. Dose escalation may continue in Part 1B up to 15 mg/kg if no MTD in Part 1A is identified.

5.4.2.1 Maximum Tolerated Dose

The MTD is defined as the highest dose associated with DLTs in Cycle 1 in less than 33% of patients receiving FPA144 administered on Day 1 and Day 15 of a planned 28-day cycle.

If the MTD is not reached during Part 1A or subsequent cycles of treatment in Part 1 provide additional insight regarding the safety profile, an RD may be selected depending on overall tolerability, PK, and estimates of efficacious exposures extrapolated from ongoing clinical evaluations.

Alternatively, the protocol may be amended to explore higher dose levels of FPA144.

5.4.2.2 Toxicity at Lowest Dose Level

If the MTD is unexpectedly exceeded at the first dose level of FPA144 (0.3 mg/kg), then decisions on how to proceed will be based on safety, tolerability, and PK data; and will be agreed on between the Investigators and Sponsor's Medical Monitor.

5.4.3 Dose Escalation within a Cohort

In Part 1 (A and B), intra-patient dose escalation will not be permitted.

In Part 2, patients will be treated at the RD as determined from Part 1 (A and B), and dose escalation will not be allowed.

5.4.4 Dose-Limiting Toxicity

DLTs are defined as any of the following events that occur during the first cycle of treatment and are assessed by the Investigator as related to FPA144. As applicable, events will be classified according to the NCI CTCAE (Version 4.03).

- Absolute neutrophil count (ANC) $<0.5 \times 10^9/L$ >5 days duration or febrile neutropenia (i.e., fever $>38.3^\circ C$ with ANC $<1.0 \times 10^9/L$).
- Platelets $<25 \times 10^9/L$ or platelets $<50 \times 10^9/L$ with bleeding requiring medical intervention
- Prolonged (>7 days) Grade 3 thrombocytopenia

- Grade 4 anemia (i.e., life-threatening consequences; urgent intervention indicated)
- Any Grade 2 or greater ophthalmologic AE that does not resolve within 7 days
- AST/ALT >3 x ULN **and concurrent** total bilirubin >2 x ULN.
- Any non-hematological AE CTCAE Grade 3 or greater (except nausea, vomiting, and diarrhea if well controlled by systemic medication). Grade 3 or 4 lab values that are not of clinical significance per Investigator and Sponsor agreement will not be considered DLTs.

Part 1A patients who experience a DLT are not required to discontinue study participation in FPA144-001.

5.4.5 Dose Modification Criteria

Dose reductions may be permitted for patients on treatment beyond the DLT period (in Part 1A) or any patient in Parts 1B or 2 per the guidelines outlined in Table 3 and Table 4 for non-ocular and ocular-related (defined as related to the cornea and retina) toxicities, respectively. If dose reductions or interruptions that do not fall within these guidelines are being considered by the Investigator, these will require discussion with and approval by the Sponsor.

Table 3: Dose Modification Guidelines (Non-corneal Toxicity)

Toxicity Grade	FPA144 Dose	Dose Schedule
1	Continue 100% of dose	No delay or missed dose required
2	Continue 100% of dose	No delay or missed dose required
3	Continue 75–100% of starting dose following recovery to Baseline or Grade 1	Up to 2 missed doses allowed without Sponsor approval to continue
4	Continue 50–75% of starting dose following recovery to Baseline or Grade 1	Up to 2 missed doses allowed without Sponsor approval to continue

Table 4: Dose Modification Guidelines for FPA144-related Corneal Toxicity

FPA144/IP-related Toxicity Grade	Dose Schedule	New FPA144 Dose
Grade 1	No Delay	100%
Grade 2	Delay dosing, see ophthalmologist and treat with topical (ophthalmologic) antibiotics	If recovery to baseline or Grade 1 within 28 days, may resume at 100% dose
Grade 2 which does not return to baseline within 28 days Any Grade 3 or Grade 4	Permanently discontinue dosing of FPA144	N/A

Any patient who reports pain or irritation of the eye or change in vision should be evaluated by an ophthalmologist.

Patients may miss up to 2 consecutive doses (up to 6 weeks between doses) for adverse or other events and may resume the study drug if the event returns to Baseline or \leq Grade 1 within 6 weeks of treatment interruption. Omission of additional dosing longer than 6 weeks for adverse events will necessitate the patient's discontinuation from the study unless allowed by the Sponsor. Patients may miss doses in the course of participation in the study, including missed doses for scheduled vacations or other personal reasons as needed, but not more than 2 doses sequentially.

There is a ± 3 -day window for the scheduled dosing visits. Patients should not have 2 consecutive doses of FPA144 within 7 days. The first dose of each cycle is considered Day 1 of each Cycle, Cycles will repeat every 28 days unless there is a treatment delay. For patients who cannot receive Day 15 treatment by Day 21, patients should skip Day 15 treatment of that cycle and resume Day 1 treatment of the next cycle. Patients can have treatment delay of Day 1 of the subsequent Cycle as long as the Day 1 treatment is within 6 weeks of the last treatment.

Intra-patient dose escalation above the starting dose for each patient will not be permitted for patients in Part 1 (A and B) and Part 2. If a patient's dose is decreased for a reason that is no longer relevant, dose escalation to the originally assigned dose may occur after discussion and approval by the Sponsor.

5.4.6 Dose Interruptions during Study Drug Infusion

Infusion of FPA144 must be stopped if any AE \geq Grade 3 occurs during the infusion. If bronchospasm or dyspnea occurs in a patient during infusion, the infusion should be stopped.

In addition, at the Investigator's discretion, the infusion rate may be reduced or stopped if a less severe AE (Grade 1 or 2) occurs during the infusion. If a Grade 3 or less severe AE resolves within 4 hours, the infusion may be restarted at half the previous rate. If the same AE appears again with the same severity at any time during the restarted infusion, the infusion should be discontinued, and no further dosing of study drug will occur without consultation with the Sponsor or Sponsor's designee.

If a patient experiences an infusion reaction, the patient's vital signs (temperature, blood pressure, pulse, and respiration rate) should be monitored during the infusion, as well as every 30 minutes after the infusion for a minimum of 2 hours and until resolution of the infusion reaction.

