Patients will be closely monitored for infusion-related reactions. The infusion length may be increased at the Investigator's discretion based on occurrence of infusion-related reactions, such as changes in vital signs, nausea, vomiting, or other constitutional symptoms or allergic reactions occurring during infusion or up to 2 hours after cessation of the infusion. For subsequent infusions, patients may be pre-medicated with antiemetics, steroids, or antihistamines at the discretion of the Investigator. The treatment will be administered according to the institution's standard practice. Epinephrine for subcutaneous injection, diphenhydramine for IV injection, and any other medications and resuscitation equipment for emergency management of anaphylactic reactions must be available in the room where the infusions are being performed. To date, four events of infusion-related reaction have been reported across three patients [one grade 1 event reported in a patient receiving FPA144 at 10 mg/kg, one grade 2 event in a patient receiving 10 mg/kg, and two events (grade 3 and 2) reported in a patient receiving 15 mg/kg] The grade 3 infusion-related event was unexpected and considered medically important per the Investigator and reported.

In summary, FGF signaling pathways appear to be valid targets for clinical investigation in human cancer based on preclinical models as well as Phase 1 clinical investigations demonstrating anti-tumor activity with broad FGFR targeted agents. Pre-clinical data support specific targeting of FGFR2b in tumors with overexpression of the receptor and non-clinical toxicology evaluation has demonstrated that potentially effective doses may be safely administered.

However, as this is the first clinical study of FPA144, the safety profile in humans has not been established, and unanticipated side effects may occur. Cautious dose escalation with close monitoring of safety is planned in this study in order to limit the risk to patients.

2. Study Objectives and Endpoints

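### Section 5.4.6: a reaction that returns worse on a restarted infusion is handled less strictly than one that returns at the same grade

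*Combined protocol and SAP*

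**What the plan says.** Section 5.4.6 sets out the handling of adverse events during an infusion in this order:

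- **Mandatory stop.** "Infusion of FPA144 must be stopped if any AE" of Grade 3 or higher occurs.
- **Named events.** "If bronchospasm or dyspnea occurs in a patient during infusion, the infusion should be stopped", whatever the grade.
- **Grade 1 or 2.** At the Investigator's discretion, "the infusion rate may be reduced or stopped if a less severe AE (Grade 1 or 2) occurs during the infusion".
- **Restart.** "If a Grade 3 or less severe AE resolves within 4 hours, the infusion may be restarted at half the previous rate". No limit on the number of restarts is given.
- **Recurrence.** "If the same AE appears again with the same severity at any time during the restarted infusion, the infusion should be discontinued". The Sponsor or its designee must then be consulted before the patient is dosed again.

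Section 5.2 on administration refers infusion handling back to Section 5.4.6. On experience so far, Section 1.9 states that "four events of infusion-related reaction have been reported across three patients": a Grade 1 event and a Grade 2 event in two patients at 10 mg/kg, and a Grade 3 and a Grade 2 event in one patient at 15 mg/kg.

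**The concern.** The recurrence rule is the only place where Section 5.4.6 requires the Sponsor to be consulted before the next dose, and it is tied to recurrence at equal severity. An event that comes back worse on same-day re-exposure, at half the rate, is the stronger warning. It should get at least the check that an unchanged event gets, and the text as written gives it less.

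What is at stake is the handling of an individual patient during an infusion and the decision to give the next dose. Sample size, error rates, endpoints and analyses are untouched.

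**Working it through.** The plan gives no figure to reproduce. The check applies the sentences of Section 5.4.6 literally to each pattern in which an event stops, resolves within 4 hours, is followed by a half-rate restart, and returns.

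| First grade → grade on restart | Stop called for? | Another restart permitted? | Sponsor consultation before next dose? |
|---|---|---|---|
| 1→1, 2→2, 3→3 | Yes (recurrence rule) | No, discontinued | Yes |
| 1→2, not bronchospasm or dyspnea | No, discretionary | Yes | No |
| 1→3, 2→3 | Yes (Grade 3 rule) | Yes, if resolved within 4 hours | No |
| 3→4 | Yes (Grade 3 or higher rule) | No, the restart sentence ends at Grade 3 | No |

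**Count within Grades 1 to 3.** Equal pairs: discontinuation and consultation in 3 of 3. Worse pairs: a stop is required in 2 of 3 (1→3 and 2→3), and consultation in 0 of 3. This counts logical cases and says nothing about how often each occurs.

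**Does another section repair it?**

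- Section 5.2 only points back to Section 5.4.6.
- Table 3 in Section 5.4.5 continues Grade 2 at full dose without delay. It lets Grade 3 resume at 75–100% and Grade 4 at 50–75% of the starting dose after recovery, with up to two missed doses before Sponsor approval is needed.
- Sections 1.9 and 5.8 leave infusion length and premedication to the Investigator.
- The 24-hour report in Section 6.2.1.5 covers serious events only, so a non-serious Grade 2 recurrence does not reach the Sponsor that way.
- The withdrawal criterion for unacceptable risk in Section 4.3 is general and rests on judgment. The DSMB review in Section 8.9 is periodic.

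None of these requires for a worse recurrence what Section 5.4.6 requires for an equal one.

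**How often could it arise?** Only an upper bound can be given, because the documents report infusion reactions but not restarts.

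- Events in Section 1.9: Grade 1 × 1, Grade 2 × 2, Grade 3 × 1. That is 4 events in 3 patients, and 3 of the 4 were at grades where stopping is discretionary.
- Assuming the 53 treated patients in Section 1.7 are the denominator: 3/53 = 5.7%, exact (Clopper-Pearson) 95% CI 1.2% to 15.7%.
- Part 2 at the October 28, 2016 cut-off: 12 (Cohort A) + 4 (E) + 10 (C) = 26, which accounts for all Part 2 patients and leaves none in Cohort F. Still to enroll: (20 − 12) + 30 = 38.
- Expected patients with any infusion reaction: 38 × 0.0566 = 2.2, range 38 × 0.0118 = 0.4 to 38 × 0.1566 = 6.0.
- If Cohort A goes to 30, as the synopsis statistics and Section 8.10 state, then (30 − 12) + 30 = 48 remain: 48 × 0.0566 = 2.7, range 0.6 to 7.5.

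Worsening after a restart would be a fraction of these. None is reported so far.

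**The case against.** The strongest case is that this is a drafting slip with an obvious meaning. A rule to discontinue on an equal recurrence would ordinarily be taken to cover a worse one. The text also applies at any time in the restarted infusion, so a reaction building from Grade 1 to Grade 2 has arguably met the trigger on the way up.

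The exposed path is narrow as well. For 1→2, the Investigator must first choose to stop for a Grade 1 event, see it resolve, restart at half rate, see it return at Grade 2, and then choose not to stop. At Grade 3 or higher the stop is mandatory. The one Grade 3 reaction was handled as serious: "The grade 3 infusion-related event was unexpected and considered medically important per the Investigator and reported". Emergency drugs must be in the infusion room, and vital signs are monitored during the infusion and for at least 2 hours after it.

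Section 5.4.5 also sends interruptions outside Tables 3 and 4 to the Sponsor for approval, which might catch an infusion abandoned at Grade 2.

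Finally, 3/53 measures any infusion reaction. It pools lower doses with the 15 mg/kg used in Part 2, although all three patients were at 10 or 15 mg/kg.

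Much of this stands. The intent was very probably equal or worse, the gap is narrow, and the 3/53 projection is no more than a loose ceiling. Three things do not stand:

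- Section 9.8 says the protocol is to be followed exactly, and Grades 1 and 2 are different severities on the CTCAE scale in Section 6.2.1.3.2. The rule should say what is meant.
- The building-up argument does not help when the event reappears directly at the higher grade.
- The Section 5.4.5 route does not apply if the infusion simply continues, and SAE reporting misses non-serious events.

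**Conclusion.** The concern holds, as a minor defect of wording in a safety rule. Read as written, Section 5.4.6 orders the cases the wrong way round. An equal recurrence leads to discontinuation and Sponsor consultation. A worse one leads to discretion (1→2) or to a stop without consultation (1→3, 2→3, 3→4), and another restart remains open in all of these except 3→4. The gap matters most for Grade 1 to 2, where neither the mandatory stop nor 24-hour reporting applies.

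The conclusion rests on a literal reading and on the absence of any other rule covering a worse recurrence. It does not depend on the frequency estimate, which assumes that the reactions in Section 1.9 arose among the 53 patients in Section 1.7 and bounds all infusion reactions, not worsening ones.

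**What to change.** In the recurrence sentence of Section 5.4.6, replace *with the same severity* by *with the same or greater severity*. This one change covers every pattern in the table: a worse recurrence would then mean discontinuing that infusion and consulting the Sponsor before any further dose. It can go into the next amendment. It adds no visits, procedures or patients, and the only running cost is an occasional Sponsor consultation before redosing.
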